Clinical Trial Registration

Study Protocol and Data Analysis Plan

Official Title: A School-based Sleep Education Program

Date: 24 July 2018

NCT ID: not yet assigned

Study Protocol

The present study aims to examine the effectiveness of a class-based interactive Sleep Education Program in improving sleep behavior of secondary school students. Participants will be randomly assigned to a Sleep Education Program or a Control Program. Participants in the Sleep Education Program will learn about the importance of sleep, what factors may prevent them from getting enough sleep, how they can manage their time to create more opportunity for sleep, and how they can overcome obstacles to time management. Participants in the Control Program will learn about various health-related topics, but will not learn about sleep. All participants will undergo four weekly class-based lessons, which use video presentations, in-class activities, discussions and take-home assignments to deliver the materials. Data will be collected on students' sleep habits, daytime functioning, mood, and time use at three time points: pre-program, immediately post-program and during a later follow-up. Sleep knowledge, habits, and attitudes towards sleep will be measured once during each time point using a sleep questionnaire. Sleep-wake patterns will be measured in two ways: objectively using actigraphy, and subjectively using sleep diaries. At each time point, participants will wear the actiwatch for one week, and during this week they will also fill in a daily sleep diary. Additionally, during the same period of one week they will rate their subjective mood and subjective sleepiness daily, and time use will be measured using a time use diary app. For this, participants are asked to chronologically log their daily activities in the diary over the one-week period. Activities recorded will be analyzed in order to find out which activities take up most of the students' time, and time spent on each activity will be correlated with data from various sleep variables, as collected by actigraphy and sleep diaries. Furthermore, time use data will be analyzed in order to assess if there are changes in the way students spend their time following the Sleep Education Program.

Statistical Analysis Plan

Primary outcome measures acquired in the current study are planned to be analyzed using SPSS Statistics (IBM) and MATLAB (MathWorks). Statistical analyzes that will be conducted include Analyses of Variance (ANOVAs), *t*-tests and correlations.

Primary Outcome Measure

1. Change in actigraphically measured sleep behavior between time 1 (pre-program), time 2 (post-program) and time 3 (follow-up), measured for one week in each of the three phases.

Actigraphy will be used to objectively measure the following sleep behavior variables: bedtime, wake up time, time in bed, total sleep time, sleep efficiency, and number and duration of daytime naps. Data will be collected daily over the period of one week, at three time points (pre-program, post-program and follow-up). ANOVAs will be used to analyze changes in each variable between and within the two groups throughout the program. The independent variables are group, time point, and their interaction. Analyses will be performed on the average within each week of data collection, as well as between each individual time point (pre-program, post-program and follow-up). Post-hoc tests will be used to compare groups.

2. Change in sleep dairy reported sleep behavior between time 1 (pre-program), time 2 (post-program) and time 3 (follow-up), recorded for one week in each of the three phases.

Sleep diaries will be used to subjectively measure the following sleep behavior variables: bedtime, wake up time, total sleep time, sleep efficiency, and number and duration of nighttime awakenings and daytime naps. Data will be collected daily over the period of one week, at three time points (pre-program, post-program and follow-up). ANOVAs will be used to analyze changes in each variable between and within the two groups throughout the program. The independent variables are group, time point, and their interaction. Analyses will be performed on the average within each week of data collection, as well as between each individual time point (pre-program, post-program and follow-up). Post-hoc tests will be used to compare groups.

3. Change in the level of subjective mood between time 1 (pre-program), time 2 (post-program) and time 3 (follow-up), measured once daily with a Mood Rating Scale over the period of one week.

Score on the mood rating scale (1-9 points) will be measured. Data will be collected once daily over the period of one week, at three time points (pre-program, post-program and follow-up). ANOVAs will be used to analyze changes in subjective mood between and within the two groups throughout the program. The independent variables are group, time point, and their interaction. Analyses will be performed on the average within each week of data collection, as well as between each individual time point (pre-program, post-program and follow-up). Post-hoc tests will be used to compare groups.

4. Change in the level of subjective sleepiness between time 1 (pre-program), time 2 (post-program) and time 3 (follow-up), measured once daily with the Karolinska Sleepiness Scale over the period of one week.

Score on the Karolinska Sleepiness Scale (1-9 points) will be measured. Data will be collected once daily over the period of one week, at three time points (pre-program, post-program and follow-up). ANOVAs will be used to analyze changes in subjective sleepiness between and within the two groups throughout the program. The independent variables are group, time point, and their interaction. Analyses will be performed on data within each week of data collection, as well as between each individual time point (pre-program, post-program and follow-up). Post-hoc tests will be used to compare groups.

5. Change in sleep knowledge, habits and attitudes between time 1 (pre-program), time 2 (post-program) and time 3 (follow-up), measured with a sleep questionnaire.

Score on the sleep knowledge questionnaire will be measured (12 questions, true or false). Data will be collected once at three time points (pre-program, post-program and follow-up). ANOVAs will be used to analyze changes in score on the sleep questionnaire between and within the two groups throughout the program. The independent variables are group, time point, and their interaction. Analyses will be performed on the average within each week of data collection, as well as between

each individual time point (pre-program, post-program and follow-up). Post-hoc tests will be used to compare groups.

6. Change in time use between time 1 (pre-program), time 2 (post-program) and time 3 (follow-up), measured daily with a time use diary over the period of one week.

Time use will be measured using a time use diary, in which activities are logged chronologically throughout the day. Data will be collected daily over the period of one week, at three time points (pre-program, post-program and follow-up). ANOVAs will be used to analyze changes in amount of time spent on different activities between and within the two groups throughout the program. The independent variables are group, time point, and their interaction. Analyses will be performed on the average within each week of data collection as well as separately for school days and free days, and also between each individual time point (pre-program, post-program and follow-up). Post-hoc tests will be used to compare changes between the two groups.

7. Relationship between sleep and time use.

Amount of time spent on each activity, measured by a time use diary, will be correlated with sleep variables, measured by actigraphy and a sleep diary, to identify types of activities that relate to short sleep. Data will be collected daily over the period of one week, at three time points (pre-program, post-program and follow-up). Pearson's or Spearman's correlations will be used to correlate scores on the different variables.

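### All seven outcome items are primary, at least 18 variables are tested separately, and nothing says which result answers the aim or how false positives are controlled

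*Combined protocol and SAP*

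**What the plan says.** The Study Protocol section states one aim: "The present study aims to examine the effectiveness of a class-based interactive Sleep Education Program in improving sleep behavior of secondary school students". It then sets out two instruments for the same construct: "Sleep-wake patterns will be measured in two ways: objectively using actigraphy, and subjectively using sleep diaries".

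In the Statistical Analysis Plan, items 1 to 7 are all numbered under Primary Outcome Measure. There is no secondary or exploratory heading.

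- **Item 1, actigraphy.** Seven variables are listed.
- **Item 2, sleep diary.** Eight variables are listed, ending with "total sleep time, sleep efficiency, and number and duration of nighttime awakenings and daytime naps". For both items, "ANOVAs will be used to analyze changes in each variable between and within the two groups throughout the program".
- **Items 3, 4 and 5.** Mood, sleepiness and a 12-question knowledge score each have their own ANOVA.
- **Item 6, time use.** ANOVAs are run on an unstated number of activities, for the weekly average "as well as separately for school days and free days".
- **Item 7.** "Relationship between sleep and time use", analysed by correlation.

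Each ANOVA contains group, time and their interaction, and comparisons between individual time points are also planned. Post-hoc tests are mentioned without a method. No alpha, testing order or multiplicity adjustment appears anywhere.

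**The concern.** A plan with one aim should say which result would answer it. Here any of 18 or more results, at either post-baseline time point, could be put forward as the primary finding once the data are in. Even the two items labelled sleep behavior hold 15 variables. Six of these measures appear in both: bedtime, wake time, total sleep time, efficiency, nap number and nap duration. The plan does not say whether actigraphy or the diary prevails if they disagree.

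Two consequences follow. First, the chance of at least one spurious primary result is well above the nominal rate. Second, and separately from chance error, outcomes that do not answer the aim have the same rank as measured sleep. Only the intervention arm is taught about sleep, so a higher knowledge score is to be expected and does not show that anyone slept differently. Item 7, as described, does not compare the arms at all.

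**Working it through.** The plan gives no alpha, sample size or error rate, so it has no figure to reproduce.

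**Step 1: count the variables with their own ANOVA (items 1 to 5).**

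| Item | Variables | Number |
|---|---|---|
| 1 | bedtime, wake time, time in bed, total sleep time, efficiency, nap number, nap duration | 7 |
| 2 | bedtime, wake time, total sleep time, efficiency, awakening number, awakening duration, nap number, nap duration | 8 |
| 3 | mood | 1 |
| 4 | sleepiness | 1 |
| 5 | knowledge score | 1 |

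7 + 8 + 1 + 1 + 1 = 18. Items 1 and 2 alone give 15. Both are floors, because item 6 adds an unstated number of activities and further splits.

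**Step 2: independent tests.** Assume two-sided 0.05 per test, one test per variable and no true effects. The chance of at least one false positive among m tests is 1 − 0.95^m.

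- m = 18: 1 − 0.95^18 = 0.603
- m = 15: 1 − 0.95^15 = 0.537

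For false positives in the favourable direction, the chance is 1 − 0.975^m: 0.366 for m = 18 and 0.316 for m = 15. The result depends on the assumed alpha: with m = 18 it is 0.166 at 0.01 and 0.850 at 0.10 in either direction.

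**Step 3: correlated tests.** Actigraphy and diary measure many of the same quantities, so independence is unlikely. With a common correlation r between the test statistics and c = 1.96, the chance is

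1 − ∫ [Φ((c − √r·u)/√(1 − r)) − Φ((−c − √r·u)/√(1 − r))]^m φ(u) du.

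For the favourable direction the second Φ term is dropped, with each variable oriented so that positive is favourable.

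| Case | r = 0 | 0.3 | 0.5 | 0.7 |
|---|---|---|---|---|
| 18 variables, either direction | 60% | 51% | 40% | 28% |
| 18 variables, favourable | 37% | 26% | 20% | 14% |
| 15 variables, either direction | 54% | 46% | 36% | 26% |
| 15 variables, favourable | 32% | 23% | 18% | 13% |

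The nominal values are 5% and 2.5%.

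**Step 4: two time points.** The plan does not choose between post-program and follow-up. Take two contrasts per variable over 18 variables, 18 × 2 = 36 tests, with an assumed correlation of 0.5 between the two contrasts. Simulation (400,000 draws) gives 82%, 73%, 61% and 45% in either direction for r = 0, 0.3, 0.5 and 0.7, and 57%, 41%, 32% and 23% in the favourable direction.

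**Step 5: what a correction would require.** If all 18 stayed co-primary, Bonferroni would set 0.05/18 = 0.0028 per test. On a normal approximation, keeping 80% power on any one test would then take about 1.87 times the sample size needed at 0.05.

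**The case against.** **The decisive test is implied.** Items 1 to 6 are framed as changes, the model includes the group-by-time interaction, and item 6 says its post-hoc tests compare change between arms. In a two-arm randomised design the interaction is the natural treatment test. That is fair, but the plan lists it level with the two main effects and describes analyses both within and between groups. Fixing on the interaction would still leave the variable and the time point open.

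**The aim narrows the field to items 1 and 2.** This is also fair, and it is why the 15-variable figures are shown. The change is small: 36% instead of 40% at r = 0.5. Taking item 1 alone, 7 variables still give 23% at r = 0.5 and 18% at r = 0.7.

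**The correlations are illustrative.** This stands. A single positive r is a simplification, since time in bed depends on bedtime and wake time, and efficiency links sleep time to time in bed. The favourable-direction figures also need an orientation that the plan does not supply, for example whether fewer naps count as an improvement. The either-direction figures do not need one. Inflation shrinks as r rises but persists: with 18 variables at r = 0.9 it is 15% in either direction, three times nominal.

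**The post-hoc tests, or the reader, may correct.** No post-hoc method is named, and one applied within a variable would not control error across 18. A reader given every p-value could apply 0.0028, but that depends on full reporting and still would not say which result answers the aim.

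**Conclusion.** The concern holds and needs to be fixed before analysis. The plan does not define what result would count as success on its own question, and that cannot be credibly settled after the data are seen. With one test per variable, the chance of at least one false positive primary result is about 28% to 60% over 18 variables and 26% to 54% over the 15 sleep-behavior variables, for correlations from 0.7 down to 0. The independence figures are the upper end of each range. These percentages rest on an assumed two-sided 0.05 and equal correlation, so they show the scale and are not properties of this trial's data. The count of 18, the single primary heading and the absence of any error control come directly from the SAP and need no assumption.

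**What to change.** Before any data are analysed, amend Primary Outcome Measure as follows.

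- **Primary.** Name one variable, one contrast and one time point from item 1. One example is actigraphic total sleep time, compared between arms at post-program with adjustment for baseline, at two-sided 0.05. Time in bed or bedtime would also fit the aim, and the choice is the sponsor's. Test the same contrast at follow-up only if the first is significant.
- **Secondary.** Move the remaining group comparisons here, with Holm or Benjamini-Hochberg adjustment within each item. List the time-use activity categories in advance.
- **Item 5.** Keep the knowledge score as a secondary check that the material was learned. Habits and attitudes stay in this item, with their scoring defined.
- **Item 7.** Label it exploratory.

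With one named primary test, the error rate for the primary claim equals the chosen alpha. The cost is SAP and registration wording; no measurement is added or dropped. The downside is that fewer outcomes can be claimed as primary and secondary p-values become less favourable. Adjustment within items does not control error across items, so secondary results should be presented as supportive.

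### Outcomes 1–6: the pre-program value is used only as a level of time; adjusting the post-hoc group comparison for it would give a more precise estimate at almost no cost

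*Combined protocol and SAP*

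**What the plan says.** The Study Protocol describes random assignment to two programs and measurement at three occasions: "pre-program, immediately post-program and during a later follow-up". In the SAP, under Primary Outcome Measure, items 1 to 6 share one model sentence: "The independent variables are group, time point, and their interaction". The opening of the SAP names ANOVAs, t-tests and correlations as methods. Neither part of the document mentions a covariate, ANCOVA or any other adjustment for the pre-program value.

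On comparing the arms, the plan has three elements:

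- The ANOVA is meant to look at change. For the actigraphy and sleep diary variables, for example: "ANOVAs will be used to analyze changes in each variable between and within the two groups throughout the program". Items 3 to 6 say the same of their own variables.
- Each of the six items adds that analyses are also made between the three occasions taken individually. No occasion is named as primary.
- Items 1 to 5 end with "Post-hoc tests will be used to compare groups", which does not say whether raw values or changes are compared. Item 6 ends with "Post-hoc tests will be used to compare changes between the two groups", which does state the scale.

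Item 7 is a correlation analysis and lies outside this point.

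**The concern.** The pre-program week can enter a comparison of randomised arms in three ways. It can be ignored (raw comparison at a later week), subtracted (difference in change), or used as a covariate (adjusted difference). The plan allows the first two and provides for no version of the third. In the full group × time ANOVA, the contrast from the pre-program week to a later week is a difference in change.

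This matters because the interaction is a test with 2 degrees of freedom. It does not say in which week, or in which direction, the arms differ. The follow-up contrast does, so readers will take their estimate of benefit from it. If it is less precise than the collected data allow, its interval is wider than it needs to be.

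**Working it through.** **Inputs.** From the documents: two randomised arms, three occasions, and a model with group, time and group × time. The documents give no sample size, SD, alpha, effect size, allocation ratio or correlation, so there is no planned figure to reproduce. Assumed: equal arms of n independent students; one correlation rho between any two occasions; two-sided 5%. For the power figures, n = 100 per arm and an effect of 0.3 SD.

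**Step 1: variance of one between-group contrast at one later week,** in units of 2·SD²/n, with equal SDs:

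- raw = 1
- change = 2(1 − rho)
- adjusted = 1 − rho²

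The saving is 1 − adjusted / min(raw, change). The interval ratio is the square root of adjusted / min(raw, change).

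| rho | raw | change | adjusted | variance saved against the better alternative | interval narrower than the better alternative |
|---|---|---|---|---|---|
| 0.3 | 1.00 | 1.40 | 0.91 | 9% (raw) | 5% |
| 0.4 | 1.00 | 1.20 | 0.84 | 16% (raw) | 8% |
| 0.5 | 1.00 | 1.00 | 0.75 | 25% (tie) | 13% |
| 0.6 | 1.00 | 0.80 | 0.64 | 20% (change) | 11% |
| 0.7 | 1.00 | 0.60 | 0.51 | 15% (change) | 8% |
| 0.8 | 1.00 | 0.40 | 0.36 | 10% (change) | 5% |
| 0.9 | 1.00 | 0.20 | 0.19 | 5% (change) | 3% |

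Example at rho 0.7: 0.51 / 0.60 = 0.85, so 15% is saved; √0.85 = 0.922, so the interval is 8% narrower.

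**Step 2: does this depend on equal SDs or large samples?** With unequal SDs, change minus adjusted is (SD_pre − rho·SD_post)², and raw minus adjusted is rho²·SD_post². Neither can be negative. Estimating the slope has a small cost. At 40 students in total it cancels the gain below about rho 0.16 (against raw) or above about 0.95 (against change); at 100 in total, below about 0.10 or above about 0.98. Simulation at rho 0.5 (8,000 runs) gave raw / change / adjusted variances of 0.98 / 1.00 / 0.75 with 50 per arm and 1.01 / 0.98 / 0.78 with 15 per arm. All three estimators were unbiased.

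**Step 3: power against the test the plan most naturally implies, the interaction.** For effects at the three occasions of (0, 0.3, 0.3), the mean is 0.2 and the squared deviations sum to 0.04 + 0.01 + 0.01 = 0.06. For (0, 0.3, 0), the mean is 0.1 and the sum is 0.01 + 0.04 + 0.01 = 0.06. The two cases therefore share one noncentrality, lambda = 100 × 0.06 / [2(1 − rho)] = 3 / (1 − rho), with 2 and 396 degrees of freedom. The adjusted post-program contrast has noncentrality 0.3 / √[2(1 − rho²)/100] on 197 degrees of freedom.

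| rho | lambda | interaction power | adjusted noncentrality | adjusted power |
|---|---|---|---|---|
| 0.5 | 6.0 | 58% | 2.45 | 68% |
| 0.6 | 7.5 | 68% | 2.65 | 75% |
| 0.7 | 10.0 | 81% | 2.97 | 84% |
| 0.8 | 15.0 | 94% | 3.54 | 94% |

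For an effect at follow-up only, (0, 0, 0.3), lambda is unchanged. The interaction keeps the power shown, while the post-program contrast rejects only at its 5% error rate.

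**Step 4: if the interaction is kept as a gate.** At rho 0.6 (20,000 simulated trials per case), the chance that the interaction and the post-program contrast are both significant, adjusted against change, was 60.2 / 59.2% for a lasting effect, 53.3 / 53.5% when half remains at follow-up, and 62.4 / 59.0% when it has gone by follow-up. Adjustment then adds little power, and the gain is mainly the interval width in Step 1.

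**The case against.** The strongest reply is that this is an efficiency preference. The planned interaction is a legitimate test in a randomised trial, and every size above rests on an assumed rho. That stands, and it limits how much weight the point can carry. It does not change the direction: for rho strictly between 0 and 1 with equal SDs, the adjusted contrast has the smallest large-sample variance, and that needs no figure from the documents.

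A second reply is that having the pre-program week as a level of time is not in itself a fault. This is also right. A longitudinal model that holds the two arms equal before the program would recover about the same precision. The plan's full group × time ANOVA imposes no such constraint, so the loss remains.

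Three stronger readings are tempting, and the documents do not support them:

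- *That the plan gives no time points for its comparisons.* It says that the individual occasions are compared with each other. What is missing is a primary occasion and, for items 1 to 5, the scale of the group comparison.
- *That adjustment brings a large gain in power.* Set against a single change contrast, the figures would be 68 / 56% at rho 0.5 and 75 / 66% at 0.6. But the plan is organised around change over three occasions, which points to the interaction. Against that test the advantage is 10 points at rho 0.5, 7 at 0.6, 3 at 0.7 and nil at 0.8. It also holds only if the effect is present at post-program.
- *That the variance falls by 30% or more at low rho.* That compares with change. Below rho 0.5 the raw comparison is the better alternative, and the saving against it is 16% at 0.4 and 9% at 0.3.

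**Conclusion.** The point holds as a matter of precision and is worth considering. No listed analysis for outcomes 1 to 6 uses the pre-program value as a covariate, and an adjusted contrast would be more precise than either form the plan allows. With equal SDs and independent students, the variance saving against the better alternative peaks at 25% at rho 0.5 and shrinks towards zero as rho approaches 0 or 1. Confidence is high in the text and the algebra, and lower in the practical benefit, because rho is unknown and may differ between outcomes and between the two later weeks.

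A reader might infer that the planned analysis is biased or that the interaction should be dropped. Neither follows. The raw, change and adjusted contrasts all estimate the same difference under randomisation, and the interaction can still pick up an effect confined to either later week.

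The choice of a primary occasion, gatekeeping, clustering by class and multiplicity across outcomes are separate issues that this point does not settle. If outcomes cluster by class, the figures above would change.

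**What to change.** For outcomes 1 to 6, replace the closing post-hoc sentence with one that states: the between-group comparison at post-program and at follow-up is the difference in means adjusted for the student's own pre-program value of the same variable, reported with a confidence interval. Fit it by ANCOVA at each later week. Alternatively, use a linear mixed model on the two later weeks with group, time, group × time, pre-program value and pre-program value × time. The last term lets the baseline slope differ between the two weeks, which is sensible because the follow-up is undated. The group × time ANOVA can stay as written.

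The cost is SAP wording; the data and the planned software (SPSS) are the same. There are two downsides: the gain is small when rho is near 0 or 1, and students with no pre-program week drop out of the adjusted contrast, so their number should be reported.

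### Outcomes 1-6 rest on a group-by-time ANOVA of unstated type; run in either usual way, it excludes students missing any time point or treats a student's repeated values as independent

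*Combined protocol and SAP*

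**What the plan says.** The Study Protocol section has data collected "at three time points: pre-program, immediately post-program and during a later follow-up". The interval to follow-up is not given. The burden on each student is heavy: "At each time point, participants will wear the actiwatch for one week, and during this week they will also fill in a daily sleep diary", with daily mood and sleepiness ratings and a chronological activity log in the same week.

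The opening of the Statistical Analysis Plan names SPSS and MATLAB and lists the methods: "Statistical analyzes that will be conducted include Analyses of Variance (ANOVAs), *t*-tests and correlations".

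Under Primary Outcome Measure, items 1 and 2 state that "ANOVAs will be used to analyze changes in each variable between and within the two groups throughout the program", and items 3-6 say much the same for their own variable. The model specification is identical in all six: "The independent variables are group, time point, and their interaction".

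The value analysed differs a little by item:
- Items 1-3: "Analyses will be performed on the average within each week of data collection, as well as between each individual time point". Item 6 also analyses weekly averages, and adds separate analyses for school days and free days.
- Item 4 (sleepiness): "Analyses will be performed on data within each week of data collection, as well as between each individual time point", with no mention of an average.
- Item 5 (questionnaire): one score per time point, so the weekly average mentioned there has no real content.

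Post-hoc tests are to follow each ANOVA. The document does not name a repeated-measures or mixed model, a covariance structure, an analysis set, or a rule for missing or incomplete weeks.

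**The concern.** A design with three repeated measurements on each student needs a model that links a student's values to one another and says what happens when one is absent. The listed terms do neither. The two ordinary ways of running an ANOVA with these terms fail differently:

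- **Classical repeated-measures ANOVA** needs a value at all three time points. A student with good pre-program and post-program data who misses follow-up leaves the interaction test and every contrast taken from that model, so observed pre-to-post data go unused.
- **Factorial ANOVA on the listed factors** keeps those values but treats three measurements from one student as if they came from three students.

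With three separate weeks of device wear and daily logging, one of them at a later follow-up, some absent weeks are to be expected. At stake are precision, the validity of the standard errors and, if loss relates to response differently in the two arms, the randomised comparison itself.

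**Working it through.** The plan has no figure to reproduce: it states no sample size, alpha, effect size, SD, correlation or expected loss. All inputs below are therefore assumptions, and the results show a range rather than a prediction for this trial.

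**1. Precision under classical repeated-measures ANOVA.** Let a fraction p be missing at each time point, independently.
- Share with all three: (1 - p)³. Share with pre and post: (1 - p)².
- Standard error ratio for the pre-to-post contrast: √[(1 - p)² / (1 - p)³] = 1/√(1 - p).

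| p | all three | pre and post | SE ratio |
|---|---|---|---|
| 10% | 0.729 | 0.810 | 1.054 |
| 15% | 0.614 | 0.722 | 1.085 |
| 20% | 0.512 | 0.640 | 1.118 |

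The standard error is thus 5%, 8% and 12% larger than needed. The ratio depends only on the loss at follow-up among students who have both pre and post. If the same students tend to miss several weeks, that loss is below p and the inflation is smaller.

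**2. Standard errors under factorial ANOVA.** Take variance 1 and an assumed within-student correlation of 0.6 between all time points.
- Change between two time points: the correct variance is 2(1 - 0.6) = 0.8, and the variance under independence is 2. SE ratio = √(2/0.8) = 1.58, so tests of change are too conservative.
- Mean over three time points: the correct variance is (1 + 2 × 0.6)/3 = 0.733, and under independence it is 1/3 = 0.333. SE ratio = √(0.333/0.733) = 0.67, so the group main effect looks more precise than it is.

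**3. Bias of the complete-case pre-to-post contrast.** Pre-to-post change c is normal with variance 0.8 (SD of the measure 1, correlation 0.6) and mean 0 in the control arm and 0.30 in the sleep arm. The probability of loss at follow-up is 1/(1 + exp(-(a + b·c))), with a set to give the stated loss. The estimate is the difference between arms in mean c among students retained.

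| Loss mechanism | Estimate (true 0.30) |
|---|---|
| Sleep arm only depends on c, b = -0.25, 20% lost per arm | 0.34 |
| Same, b = -0.5 | 0.38 |
| Same, b = -1 | 0.44 |
| Same, b = -1, 10% lost per arm | 0.37 |
| Same, b = -1, 30% lost in sleep arm, 15% in control | 0.51 |
| Both arms depend on c, equal b, 20% lost in each | 0.30 |
| One common rule (equal a and b = -1), 20% lost overall | 0.27 |

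The sixth row is unbiased because retention shifts the mean change by the same amount in both arms. The seventh is attenuated because one common rule removes fewer students from the arm that improves more. With a true effect of zero, a common rule gives no bias.

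**4. Does the alternative repair it?** In all rows above, using every student with pre and post returns 0.30, since loss is at follow-up and depends only on observed change. A separate simulation (20,000 students, true effect 0.40 SD at both later time points, about 20% loss, dependence in the sleep arm only, b = -1) gave complete-case contrasts of 0.53 pre-to-post and 0.46 pre-to-follow-up. A mixed model with a random student intercept on all available data gave 0.40 for both.

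**The case against.** The strongest reply is that the plan never says it will run a repeated-measures ANOVA or delete incomplete students. The same three fixed effects can be fitted as a linear mixed model in SPSS or MATLAB, which keeps incomplete students. On this view the plan is only silent on detail. Part of that stands. A reader might infer that the plan drops every student without all three weeks; the documents do not support this as a fact, because the ANOVA type is not named. But ANOVA is what is named, a mixed model is not, and nothing in the text steers the analyst away from either failing form.

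A reader might also infer that the pre-to-post comparison is certain to lose students who miss follow-up. That is not established either. The SAP separately plans t-tests and analyses between individual time points, and these could keep every pre/post pair. The plan does not say which students enter them, and the interaction test would still be affected under a classical repeated-measures ANOVA.

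A third tempting inference is that any loss related to response inflates the program effect. The figures above contradict it: equal dependence and equal loss in both arms leave the estimate at about 0.30, and a common rule lowers it. Direction and size turn on how loss differs between arms, which the documents do not address.

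The lessons are class-based and the unit of random assignment is not clear, so within-student correlation may not be the only kind to model. That is a separate question. It does not weaken this one, but the model proposed here does not settle it.

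**Conclusion.** The point holds in conditional form. The analysis named for outcomes 1-6 is under-specified, and each of the two usual ways of running it has a definite fault: exclusion of students missing any time point (for outcome 5, any questionnaire), or wrong standard errors. This is more than a missing sentence on missing data, since such a sentence would not choose between the two forms; the model itself has to be named.

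The size in this trial cannot be computed. On assumed, independent loss of 10-20% per time point, the avoidable inflation of the pre-to-post standard error is 5-12%, and less if absences cluster in the same students. Bias of 0.08 to 0.14 SD on a true 0.30 SD (estimates 0.38-0.44) requires 20% loss per arm, a correlation of 0.6 and response-dependent loss confined to the sleep arm at log-odds slopes of -0.5 to -1. A milder slope or lower loss gives less, more loss in the sleep arm gives more, and a common loss rule can attenuate the effect. The change is worth making before data are seen, because it is cheap and removes discretion over which students count.

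**What to change.** For outcomes 1-6, replace the ANOVA by a linear mixed model, available in the SPSS software already planned. Fit it to each student's value per time point (the weekly average, or the single score for outcome 5), with fixed effects for group, time point and their interaction, and an unstructured covariance across the three time points within student. Include every randomised student with at least one usable time point, in the assigned group. Take the between-group pre-to-post and pre-to-follow-up contrasts from this model.

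Three short additions complete it: define a usable week by a minimum number of valid days, say which students enter any t-test or pairwise analysis that is retained, and add a sensitivity analysis for missing data.

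The cost is SAP wording and slightly more analysis work. The small downside is reliance on missing-at-random: if loss depends on values never observed, the mixed model can be biased too, which is what the sensitivity analysis is for.
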